***Week 16 through Week 52 (Withdrawal and Retreatment Period)***

- **Group Ia:** Participants randomized to guselkumab who are PASI 90 responders at Week 16 will not receive any additional doses of guselkumab until they lose  $\geq 50\%$  of their Week 16 PASI improvement, at which time they will receive a weight-based guselkumab SC dose, followed by a dose 4 weeks later, and q8w thereafter through Week 52.
- **Group Ib:** Participants randomized to guselkumab who are PASI 90 nonresponders at Week 16 will receive a placebo SC injection at Week 16 and continue treatment with guselkumab SC q8w from Week 20 through Week 52.
- **Group IIa:** Participants randomized to placebo who are PASI 90 responders at Week 16 will not receive any additional doses of study intervention until they lose  $\geq 50\%$  of their Week 16 PASI improvement, at which time they will receive a weight-based guselkumab SC dose, followed by a dose 4 weeks later, and q8w thereafter through Week 52.
- **Group IIb:** Participants randomized to placebo who are PASI 90 nonresponders at Week 16 will receive a weight-based guselkumab SC dose at Weeks 16 and 20, followed by q8w dosing thereafter through Week 52.
- **Group III:** Participants randomized to etanercept who elect to continue in the study will receive a weight-based guselkumab SC dose at Weeks 20 and 24, followed by q8w dosing thereafter through Week 48.

Participants in any of the treatment groups who elect to end study participation at Week 52 and not participate in the LTE will not receive any administration of study intervention at Week 52 and should return to the site 12 weeks after receiving the last administration of study intervention for a safety follow-up visit.

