2.4.2. Safety Analysis Set

Safety analyses for both Part 1 and Part 2 will be performed on the safety analysis set, which is defined as all treated subjects who received at least 1 injection of study agent (partial or complete). For the safety analyses in Part 1, subjects will be analyzed according to the actual treatment received during the study irrespective of the treatment assigned at randomization.

Safety analyses for LTE will be performed on the safety analysis set including all subjects who entered into LTE and received at least 1 injection at or after Week 52.

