7. SAFETY

Safety will be assessed by summarizing the incidence and type of AEs and examining changes in laboratory parameters (hematology and chemistry), vital signs, and suicidal ideation and behavior.

In the safety analyses for Part 1, subjects who were randomized and received at least 1 (partial or complete) dose of study agent administration will be included and analyzed according to the treatment they actually received, regardless of the treatment assigned at randomization. No formal statistical comparison is planned.

For Part 2, the safety analyses will be performed for all subjects enrolled in Part 2 and treated.

For LTE, the safety analyses will be performed for all subjects entered in LTE and treated at or after Week 52.

Depending on the safety data categories, the cumulative safety data will be analyzed through different study periods which include but are not limited to through Week 16, through Week 52, and through the LTE as appropriate. Unless otherwise specified, tabular summaries of safety events for key study periods are in general presented as follows:

Summaries through Week 16 (placebo-controlled period in Part 1):

Safety data through Week 16 will be summarized by treatment groups:

- Placebo
- Guselkumab
- Etanercept

This allows between-group comparisons of safety between the guselkumab group, etanercept group and the placebo group based on similar follow-up period in each group.

Summaries through Week 52 in Part 1

Safety data through Week 52 will be summarized by treatment group defined as follows:

1. **Placebo → Guselkumab:** all subjects who were randomized to placebo at Week 0, started treatment with placebo only, and later crossed over to receive treatment with guselkumab. Only the safety events/measurements from these subjects that occurred on or after their first administration of guselkumab will be included in this group.

2. **Guselkumab:** all subjects who were randomized to guselkumab at Week 0 and were treated with guselkumab. All the safety events/measurements from these subjects that occurred beginning at Week 0 will be included in this group.
3. **Etanercept → Guselkumab:** all subjects who were randomized to etanercept at Week 0, started treatment with etanercept only, and later crossed over to receive treatment with guselkumab. Only the safety events/measurements from these subjects that occurred on or after their first administration of guselkumab will be included in this group.

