4. **Combined Guselkumab:** all subjects as described above in the Placebo → Guselkumab, the Etanercept → Guselkumab and the Guselkumab groups.

In addition, the summaries of selected AE rates per hundred subject-years of follow-up through Week 52 will be provided.

Selected safety analyses will also be performed after retreatment with guselkumab among subjects who were randomized to guselkumab at Week 0, were PASI 90 responders at Week 16, were withdrawn from and then retreated with guselkumab.

Summaries through Week 52 in Part 2

Safety data through Week 52 will be summarized for all subjects who were enrolled in Part 2 and received at least 1 study agent administration of guselkumab. All the safety events/measurements from these subjects that occurred beginning at Week 0 will be included in this group.

Summaries through the LTE

Safety data through the LTE will be summarized for all subjects who participated in the LTE and were treated with guselkumab. All the safety events/measurements from Week 52 through the end of the study will be included in this group.

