7.1. Adverse Events

The verbatim terms used in the CRF by investigators to identify adverse events will be coded using the Medical Dictionary for Regulatory Activities (MedDRA version xx). Any AE occurring at or after the initial administration of study agent through the end of the trial is considered to be treatment emergent. If the event occurs on the day of the initial administration of study agent, and either event time or time of administration are missing, then the event will be assumed to be treatment emergent. If the event date is recorded as partial or completely missing, then the event will be considered to be treatment emergent unless it is known to be prior to the first administration of study agent based on partial onset date or resolution date. All reported treatment-emergent adverse events will be summarized by MedDRA system organ class, preferred term, and actual treatment group. The numbers of subjects reporting at least 1 event of the following treatment emergent AE categories will be summarized.

- AEs
- Serious AEs (SAEs)
- AEs leading to discontinuation of study agent

- AEs by severity
- AEs by relationship to study agent
- Infections
- Serious infections
- Infections treated with oral or parenteral antimicrobial treatment
- Injection-site reactions

In addition to the summary tables, listings will be provided for subjects who:

- Had SAEs
- Had AEs leading to discontinuation of study agent
- AEs of psoriasis
- AEs of severe intensity
- Serum sickness-like reactions and anaphylactic reactions

These summary tables will provide the count and percentage of subjects with 1 or more of the specified AEs by treatment group. The AEs and infections will also be summarized by age group through Week 16 and through Week 52 for Part 1. To adjust for the different duration of follow-up among treatment groups, number of events per hundred subject-years of follow-up through Week 52 will also be provided for all AEs.

Any unfavorable or unintended sign that occurs at the injection site is an injection site reaction and will be recorded as an injection site reaction by the investigator on the eCRF. An infection is defined as any AE that was recorded as an infection by the investigator on the eCRF.

The treatment-emergent adverse events of psoriasis include any event of erythrodermic psoriasis, pustular psoriasis, guttate psoriasis, and worsening or exacerbation of psoriasis. A listing of these events will be provided.

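### No safety table defined in SAP 7 covers adverse events after Week 52 in guselkumab-treated participants who do not enter the long-term extension, although SAP 7.1 promises a summary of all treatment-emergent events

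*SAP*

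**What the plan says.** SAP 7 (Safety) sets out tables by period and population. After the Week 16 tables, Part 1 has one further window: "Safety data through Week 52 will be summarized by treatment group defined as follows". The groups are placebo to guselkumab, guselkumab, etanercept to guselkumab, and combined guselkumab. Part 2 has the same end point: "Safety data through Week 52 will be summarized for all subjects who were enrolled in Part 2". Beyond that there is only the extension: "Safety data through the LTE will be summarized for all subjects who participated in the LTE and were treated with guselkumab". For that group, "All the safety events/measurements from Week 52 through the end of the study will be included in this group". SAP 2.4.2 confirms the restriction, defining the LTE safety set as "all subjects who entered into LTE and received at least 1 injection at or after Week 52".

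SAP 7.1 is wider. "Any AE occurring at or after the initial administration of study agent through the end of the trial is considered to be treatment emergent", and it goes on to commit to tabulating every reported treatment-emergent event. Event rates per hundred subject-years are specified only through Week 52.

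Protocol 6.1 says that Part 1 participants who end at Week 52 "will not receive any administration of study intervention at Week 52 and should return to the site 12 weeks after receiving the last administration", and gives the same rule for Part 2. Protocol 8.3.1.1 collects AEs until the participant's last study-related procedure, so events up to that visit are in the database.

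**The concern.** The definition of a treatment-emergent event runs to the end of the trial, but the tables meant to count such events do not reach that far for everyone. The 12-week visit exists to observe children after the last dose. For non-entrants dosed late in the year, part of that window lies after Week 52. If the tables are programmed as written, those events have no row and the time at risk has no denominator.

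Three features make this more than a drafting gap:

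- **Selection.** Protocol 6.1 and 8 make LTE entry depend on a beneficial response as judged by the investigator (Protocol 4.1 says only that all completers will be offered it). Inadequate responders are therefore likely to be among the non-entrants.
- **Timing.** The Week 52 database lock is tied to the last Week 52 visit, not to the later follow-up visits. Late enrollees' final visit may come after it. The remaining planned lock is at the end of the study, and the safety table defined for that period is confined to the LTE.
- **Pattern.** SAP 4.5 does the same for protocol deviations: after Week 52 they are summarized only for participants who continued into the LTE.

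With about 100 exposed children, a few events can shift a rate.

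**Working it through.** **Inputs.** Dosing schedules: Protocol 6.1. Stated last Part 2 injection, Week 44: Protocol 4.2. Follow-up visit 12 weeks after last dose, with no Week 52 dose for non-entrants: Protocol 6.1 and footnotes to 1.3.1 and 1.3.2. Table windows: SAP 7.

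**Reproducing the plan's figure.** Part 2 doses fall at Weeks 0, 4, then every 8 weeks: 12, 20, 28, 36, 44, 52. Dropping Week 52 leaves Week 44 as the last, which agrees with Protocol 4.2.

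**Weeks outside the Week 52 window.** With last dose at Week L, the visit is at L + 12, and the weeks beyond the window are max(0, L + 12 − 52).

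| Group (not entering the LTE) | Doses from guselkumab start | Last | Visit | Weeks after 52 |
|---|---|---|---|---|
| Part 2; Group Ib | 0, 4, 12, 20, 28, 36, 44 | 44 | 56 | 4 |
| Group IIb | 16, 20, 28, 36, 44 | 44 | 56 | 4 |
| Group III | 20, 24, 32, 40, 48 | 48 | 60 | 8 |
| Responders (re)treated from Week 24, 32 or 40 | then +4, then every 8 | 44 | 56 | 4 |
| Responders (re)treated from Week 20, 28, 36, 44 or 48 | then +4, then every 8 | 48 | 60 | 8 |
| Anyone last dosed at Week 40 or earlier | – | ≤40 | ≤52 | 0 |
| Guselkumab responders never retreated | 0, 4, 12 | 12 | 24 | 0 |

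So 4/12 = 33% or 8/12 = 67% of the planned follow-up falls after Week 52, or none of it.

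**Matching against the defined tables.** The Part 1 and Part 2 tables end at Week 52. The LTE table requires LTE entry and an injection at or after Week 52; a non-entrant has neither. No defined period table is left.

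**Partial cover from the retreatment analysis.** SAP 7.1 analyses AEs, infections and injection-site reactions within 16 weeks of retreatment, for participants withdrawn from guselkumab at Week 16. Retreatment at Week 40, 44 or 48 gives windows to 56, 60 and 64, which reach the follow-up visits at 56, 60 and 60. Retreatment at Week 36 gives 36 + 16 = 52, so nothing beyond Week 52. Part 2 and Groups Ib, IIb and III are outside this analysis.

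**Size.** The number of non-entrants is not in the documents. For n non-entrants losing w weeks, subject-years = n × w / 52:

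- n = 10: 10 × 4/52 = 0.77 to 10 × 8/52 = 1.54
- n = 20: 20 × 4/52 = 1.54 to 20 × 8/52 = 3.08
- wider range, 5 to 40 of 100: 5 × 4/52 = 0.38 to 40 × 8/52 = 6.15

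For scale, take the minimum sample sizes, full completion, and crossover at Week 16 (placebo) and Week 20 (etanercept). Guselkumab-group follow-up to Week 52 is then (40 × 52 + 25 × 36 + 25 × 32 + 10 × 52) / 52 = 4,300 / 52 = 82.7 subject-years. The 10-to-20 range is 0.77/82.7 = 0.9% to 3.08/82.7 = 3.7% of that.

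**The case against.** A reader might infer that these events go unreported. The documents do not support that:

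- SAP 7.1's commitment to summarize all treatment-emergent events carries no Week 52 limit, and Protocol 9.4.3 includes all reported AEs in the analysis.
- SAP 7 leaves its list of periods open and describes its layout as the general one.
- SAP 7.1 lists serious AEs, severe AEs, AEs leading to discontinuation, AEs of psoriasis, and serum sickness-like and anaphylactic reactions, with no time limit. SAP 7.4.1 does the same for suicidal ideation, suicidal behavior and self-injury.

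All of this stands. It does not close the gap. An open list permits another table but does not fix its population, window or denominator. The general commitment is one that the defined tables cannot meet. Listings give neither percentages nor rates, and they omit non-serious, non-severe AEs, including most infections.

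The Week 52 tables might also have been meant to include the follow-up visit. The protocol's schedules through Week 52 contain the termination visit, and SAP 7 includes events from Week 0 in the guselkumab and Part 2 groups without giving an end date in that sentence. This is plausible but nowhere stated, and the main study is defined as ending at the last Week 52 visit.

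Finally, the affected time is small and the safety analysis is descriptive. That is fair, and it limits the weight of the point.

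**Conclusion.** The point holds as a mismatch between SAP 7.1 and the tables in SAP 7. For non-entrants last dosed at about Week 44 or Week 48, 4 or 8 of the 12 follow-up weeks have no defined period table, apart from the retreatment analysis for those retreated late. The loss is mainly in tabulated counts and rates of non-serious, non-severe AEs. On the assumption of 10 to 20 non-entrants among about 100 exposed, it is about 0.8 to 3.1 subject-years; the upper end needs all 20 to have been last dosed at Week 48.

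Two stronger readings should be resisted. One is that the gap hits everyone who stops treatment: participants who stop by Week 40 have their whole 12 weeks inside Week 52. The other is that the AE counts are biased in guselkumab's favour: entry does depend on judged benefit, but no document gives the number of non-entrants, their reasons or their tolerance, so the direction is unknown.

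The change is worth making because the data are already collected and the window would otherwise be chosen after the sponsor is unblinded at the Week 16 lock.

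**What to change.** Either of two changes to SAP 7 would do:

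1. Define the Week 52 guselkumab safety tables for Part 1 and Part 2 as running through Week 52 or, for participants not entering the LTE, through the final safety follow-up visit, with subject-years counted over the same interval.
2. Add an end-of-study table for all guselkumab-treated participants, from first guselkumab dose to last visit, covering both parts.

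Under the first option, the SAP should also say how follow-up visits after the Week 52 lock will be added. The cost is SAP wording, slightly more table work and slightly higher counts. No new data and no design change are needed.

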7.1. Adverse Events

The verbatim terms used in the CRF by investigators to identify adverse events will be coded using the Medical Dictionary for Regulatory Activities (MedDRA version xx). Any AE occurring at or after the initial administration of study agent through the end of the trial is considered to be treatment emergent. If the event occurs on the day of the initial administration of study agent, and either event time or time of administration are missing, then the event will be assumed to be treatment emergent. If the event date is recorded as partial or completely missing, then the event will be considered to be treatment emergent unless it is known to be prior to the first administration of study agent based on partial onset date or resolution date. All reported treatment-emergent adverse events will be summarized by MedDRA system organ class, preferred term, and actual treatment group. The numbers of subjects reporting at least 1 event of the following treatment emergent AE categories will be summarized.

- AEs
- Serious AEs (SAEs)
- AEs leading to discontinuation of study agent

- AEs by severity
- AEs by relationship to study agent
- Infections
- Serious infections
- Infections treated with oral or parenteral antimicrobial treatment
- Injection-site reactions

In addition to the summary tables, listings will be provided for subjects who:

- Had SAEs
- Had AEs leading to discontinuation of study agent
- AEs of psoriasis
- AEs of severe intensity
- Serum sickness-like reactions and anaphylactic reactions

These summary tables will provide the count and percentage of subjects with 1 or more of the specified AEs by treatment group. The AEs and infections will also be summarized by age group through Week 16 and through Week 52 for Part 1. To adjust for the different duration of follow-up among treatment groups, number of events per hundred subject-years of follow-up through Week 52 will also be provided for all AEs.

Any unfavorable or unintended sign that occurs at the injection site is an injection site reaction and will be recorded as an injection site reaction by the investigator on the eCRF. An infection is defined as any AE that was recorded as an infection by the investigator on the eCRF.

The treatment-emergent adverse events of psoriasis include any event of erythrodermic psoriasis, pustular psoriasis, guttate psoriasis, and worsening or exacerbation of psoriasis. A listing of these events will be provided.

Psoriasis rebound will be assessed during the withdrawal period for subjects withdrawn from guselkumab at Week 16. Psoriasis rebound is defined as an event of new erythrodermic or pustular psoriasis, or a PASI of $\geq 125\%$ of the baseline PASI (ie, a worsening of PASI by 25% or greater from baseline) that occurred during the withdrawal period from the time subjects are withdrawn from guselkumab at Week 16.

In addition, safety will be assessed for subjects who are withdrawn from guselkumab at Week 16 and subsequently retreated upon loss of response. These analyses will include safety categories of AE, infection, and injection site reaction within 16 weeks after retreatment.

Since safety should be assessed relative to exposure and follow-up, most AE summary tables will include average weeks of follow-up and average number of study agent administrations for each treatment group.

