**Long-term Extension (From Week 52 until study termination)**

Following completion of the Week 52 visit, participants who have had a beneficial response from guselkumab treatment as determined by the investigator, and are willing to continue guselkumab treatment, may enter the LTE of the study. Participants who decide to participate in the LTE will continue to receive guselkumab at Week 52 and q8w thereafter until one of the following occurs:

- The participant turns 18 years of age and resides in a country where marketing authorization has been granted for guselkumab treatment of plaque psoriasis in adult patients, and have had the opportunity to complete up to 1 year in the LTE.
- Marketing authorization is obtained for guselkumab for treatment of plaque psoriasis for patients  $\geq 6$  to  $< 18$  years of age in the participant's country of residence.
- Marketing authorization is denied for guselkumab for the treatment of plaque psoriasis for patients  $\geq 6$  to  $< 18$  years of age in the participant's country of residence.
- A company decision is made to no longer pursue an indication in plaque psoriasis in the pediatric population ( $\geq 6$  to  $< 18$  years of age) in the participant's country of residence.

Participants in Part 1 who continue in the LTE portion of the study will receive guselkumab as follows:

- Participants withdrawn from guselkumab or placebo at Week 16 who meet loss of response criteria and are retreated with or initiated guselkumab prior to Week 52 and receive guselkumab at Week 48 will not receive study intervention administration at Week 52 and will resume guselkumab administration at Week 60 and q8w thereafter.
- Participants who meet loss of response criteria at Week 48 will receive guselkumab at Weeks 48 and 52 followed by q8w administration beginning at Week 60.
- Participants withdrawn from treatment at Week 16 who have not been retreated with guselkumab prior to Week 52 will receive a weight-based guselkumab dose at Week 52 and q8w thereafter.

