## Adverse Events

The verbatim terms used in the CRF by investigators to identify adverse events will be coded using MedDRA. Intervention-emergent adverse events are adverse events with onset during the intervention phase or that are a consequence of a pre-existing condition that has worsened since baseline. All reported adverse events will be included in the analysis. For each adverse event, the percentage of participants who experience at least 1 occurrence of the given event will be summarized by intervention group. Safety will be summarized separately for Part 1 and Part 2.

Summaries, listings, datasets, or participant narratives may be provided, as appropriate, for those participants who die, who discontinue intervention due to an adverse event, or who experience a severe or a serious adverse event.

The following analyses will be used to assess the safety of participants in the study:

- The incidence and type of AEs.
- The incidence and type of SAEs.
- The incidence and type of related AEs as assessed by the investigator.
- The incidence and type of injection site reactions.
- The incidence of infections.
- The incidence AEs of psoriasis.

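### Adverse event rates per 100 subject-years are specified only through Week 52; the open-ended extension gets counts and percentages with average follow-up, but no exposure-adjusted rate

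*SAP*

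**What the plan says.** Two places in the SAP specify subject-year rates. Section 7.1 promises them for all adverse events, "number of events per hundred subject-years of follow-up through Week 52 will also be provided for all AEs", and gives the reason as differing follow-up between treatment groups. Section 7, under the Week 52 summaries for Part 1, adds that "the summaries of selected AE rates per hundred subject-years of follow-up through Week 52 will be provided". Both stop at Week 52.

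The default measure has no time component. The SAP states: "These summary tables will provide the count and percentage of subjects with 1 or more of the specified AEs by treatment group". The protocol's safety analysis section agrees: "the percentage of participants who experience at least 1 occurrence of the given event will be summarized by intervention group".

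For the LTE, Section 7 defines the population, "For LTE, the safety analyses will be performed for all subjects entered in LTE and treated at or after Week 52", and the window, "All the safety events/measurements from Week 52 through the end of the study will be included in this group". It names no rate.

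Two other provisions reach into the LTE. The end of SAP 7.1 says that safety should be judged against exposure and follow-up, and puts average weeks of follow-up and average number of administrations in most adverse event tables. SAP 4.4 summarizes exposure through the LTE. Neither is limited to Week 52.

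Individual LTE follow-up has no fixed length. Under Protocol 6.1 it can end when "The participant turns 18 years of age and resides in a country where marketing authorization has been granted" for adults (with the opportunity for up to 1 year in the LTE), or when "Marketing authorization is obtained for guselkumab for treatment of plaque psoriasis for patients" in the pediatric age range in the country of residence. It can also end when that authorization is denied, or by company decision.

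**The concern.** The plan applies its adjustment for unequal follow-up where follow-up is bounded, and leaves it out where follow-up is open-ended. LTE duration depends on age, country and regulatory outcome, so it can differ widely between participants. A percentage with at least one event rises with time even when the underlying risk is constant.

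Two things are at stake, both descriptive. First, a reader who sees a higher percentage in the LTE than at Week 52 cannot tell from it whether risk has risen or observation was longer. Second, the Week 52 rate counts events, while the LTE percentage counts subjects. A child with several infections and a child with one contribute equally to the percentage, so recurrence drops out of the LTE summary.

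**Working it through.** The documents give no LTE durations and no pediatric adverse event rates, so there is no planned figure to reproduce. The rates and LTE durations below are assumptions, chosen to show the range.

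**Step 1. Spread of follow-up where rates are specified.** Safety events in the crossover groups count from the first guselkumab dose (SAP 7). Planned follow-up on guselkumab to Week 52 is therefore:
- randomized to guselkumab: 52 weeks
- placebo nonresponders, starting at Week 16: 52 − 16 = 36 weeks
- etanercept, starting at Week 20: 52 − 20 = 32 weeks

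The largest ratio among these is 52/32 = 1.6. Placebo responders who start guselkumab later have less. In the LTE there is no planned maximum.

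**Step 2. Effect of duration alone on a percentage.** With a constant rate, the share with at least one event by time T is 1 − exp(−rate × T). For example, at 20 per 100 subject-years: 1 − exp(−0.20 × 1) = 18.1% and 1 − exp(−0.20 × 5) = 63.2%.

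| Assumed rate per 100 subject-years | 1 year | 2 years | 3 years | 5 years |
|---|---|---|---|---|
| 2 | 2.0% | 3.9% | 5.8% | 9.5% |
| 5 | 4.9% | 9.5% | 13.9% | 22.1% |
| 20 | 18.1% | 33.0% | 45.1% | 63.2% |
| 50 | 39.3% | 63.2% | 77.7% | 91.8% |
| 100 | 63.2% | 86.5% | 95.0% | 99.3% |

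From 1 to 5 years the percentage for the rarest event grows 9.5/2.0 = 4.75-fold with no change in risk. Total events divided by total subject-years has the same expected value in every column of a row.

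**Step 3. Whether average follow-up closes the gap.** Suppose half the subjects are followed 1 year and half 4 years, a mean of 2.5 years. The percentage in the table is p = 0.5 × [1 − exp(−rate × 1)] + 0.5 × [1 − exp(−rate × 4)]. A reader with p and the mean can work back to −ln(1 − p)/2.5.

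| True rate per 100 subject-years | Percentage shown | Rate read back |
|---|---|---|
| 2 | 4.8% | 2.0 |
| 5 | 11.5% | 4.9 |
| 20 | 36.6% | 18.2 |
| 50 | 62.9% | 39.7 |
| 100 | 80.7% | 65.8 |

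The reading is accurate for rare events and about one third too low at 100 (65.8/100 = 0.66).

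**Step 4. What the planned tables contain.** Number of subjects × average weeks of follow-up gives total subject-time, so the denominator of an event rate is already there. The number of events is not, because the specified count is of subjects. For recurrent events no calculation from the percentage can supply it.

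**The case against.** The strongest reply is that the SAP's reason for rates does not carry over. Rates are there to adjust for follow-up that differs between treatment groups, and the LTE is summarized as one open-label guselkumab group. No between-group comparison in the LTE can be biased, and no formal safety comparison is planned even for Part 1. This stands: the point concerns interpretation only. The Section 7 rate sentence also sits under a Part 1 Week 52 heading, so its limit follows from its place. Only the sentence in 7.1 is general.

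The second reply is that the LTE percentages do not stand alone. Average follow-up and administrations appear in most tables, exposure is summarized through the LTE, and serious events, discontinuations and severe events are listed by subject. For infrequent events this is enough, as Step 3 shows. For common or recurrent events it is not.

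Third, Section 7 describes its presentations as general and non-exhaustive, so LTE rates are not excluded. True, but they are not committed to either, and the measure is better fixed before the data are seen.

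A reader might infer more: that LTE percentages will mainly reflect how long people stayed. The documents do not support this, because it depends on the distribution of follow-up and on event rates, and neither is given. The amendment dates from 2017 to 2024 do not fill that gap. Enrollment was staged behind Week 16 reviews and each participant has 52 weeks before the LTE, so calendar span is not LTE duration.

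**Conclusion.** The gap is real and modest. The SAP covers the end-of-study lock but specifies no exposure-adjusted adverse event rate for the period after Week 52, where individual follow-up is open-ended. Average follow-up is adequate context for rare events. It does not recover rates for common or recurrent ones, and it does not put the LTE in the same units as the Week 52 results.

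The size is illustrative. Under assumed constant rates of 2 to 100 per 100 subject-years and durations of 1 to 5 years, duration alone changes a percentage by up to nearly 5-fold. Under an assumed mix of 1 and 4 years, the back-calculated rate runs from almost exact to about one third too low. If actual LTE durations prove similar across participants, the back-calculation error shrinks, but the loss of recurrence and the mismatch of units remain.

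No hypothesis test, estimand or randomized comparison is affected. The change is worth making because it is specific, nearly free and uses the SAP's own measure.

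**What to change.** In SAP 7.1, extend the subject-year rate statement so that it covers the period through Week 52 and the LTE. In the LTE summaries in Section 7, add the number of events per 100 subject-years for adverse events, serious adverse events, infections, serious infections and adverse events leading to discontinuation of study agent.

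Confidence intervals are optional. If shown, use exact Poisson intervals only for first-event incidence rates (subjects with an event divided by subject-years at risk). Total event counts include repeat events within a subject, and a Poisson interval on them would be too narrow for recurrent adverse events and infections. For those, use a method that allows for within-subject repetition.

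The cost is SAP wording and one added column in the LTE tables. The events and follow-up needed are already collected, and no new data are required.
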